8.7.1 Prohibited Therapies

Immunosuppressive treatment is prohibited during the study. Use of topical calcineurin inhibitors or steroids on MC or within 2 cm of MC lesions is prohibited within 14 days of baseline and during the study. Use of the following concomitant medications to treat MC 14 days prior to baseline and during the study is prohibited: podophyllotoxin, imiquimod, cantharidin, sinecatechins, topical retinoids, oral or topical zinc, other homeopathic or over-the-counter products including, but not limited to, ZymaDerm and tea tree oil, cimetidine and other histamine H2 receptor antagonists. Surgical procedures to treat MC (e.g. cryotherapy, curettage) are prohibited during the study. The CRO medical monitor should be contacted for any questions regarding prohibited therapies.

9 SAFETY MONITORING

Adverse events will be assessed and collected after the initiation of study drug treatment through the end of the subject's last visit. In order to avoid bias in eliciting AEs, subjects/caregivers should be asked the following non-leading question: "How have you felt since your last visit?" SAEs will be collected from the time of consent through the end of the subject's last visit. Adverse events that occur from time of consent up to the time of treatment administration should be recorded as medical history for all participants. Serious adverse events will be followed until resolution.

9.1 Definitions

- Adverse event – An AE is any untoward medical occurrence associated with the use of an intervention in humans whether or not it is considered intervention-related.
- Serious adverse event (SAE) – An event is considered "serious" if, in the view of either the investigator or sponsor, it results in any of the following outcomes:
 - Death
 - A life-threatening AE (An event is considered "life-threatening" if, in the view of either the investigator or sponsor, its occurrence places the patient or subject at

- immediate risk of death. It does not include an AE or suspected adverse reaction (AR) that, had it occurred in a more severe form, might have caused death.)
- Inpatient hospitalization or prolongation of existing hospitalization
 - A persistent or significant incapacity or substantial disruption of the ability to conduct normal life functions
 - A congenital anomaly/birth defect
 - Important medical events that may not result in death, be life-threatening, or require hospitalization may be considered serious when, based upon appropriate medical judgment, they may jeopardize the patient or subject and may require medical or surgical intervention to prevent one of the outcomes listed in this definition. Examples of such medical events include allergic bronchospasm requiring intensive treatment in an emergency room or at home, blood dyscrasias or convulsions that do not result in inpatient hospitalization, or the development of drug dependency or drug abuse.
- Causality or relatedness – Determination of whether there is a reasonable possibility that the product is causally related to the adverse event. Causality assessment includes, for example, evaluation of temporal relationships, dechallenge/rechallenge information, association with (or lack of association with) underlying disease, presence (or absence) of a more likely cause, and biologic plausibility.
 - Adverse reaction – An AR is any AE caused by a drug.
 - Suspected adverse reaction (SAR) – An SAR is any AE for which there is a reasonable possibility that the drug caused the AE. For the purposes of IND safety reporting, “reasonable possibility” means there is evidence to suggest a causal relationship between the drug and the AE. SAR implies a lesser degree of certainty about causality than AR.
 - Unexpected – An event is considered unexpected if it is not listed in the IB, is not listed at the specificity or severity that has been observed, or, if an IB is not required or available, is not consistent with the risk information described in the General Investigational Plan or elsewhere in the IND. Unexpected also refers to events that are mentioned in the IB as occurring with a class of drugs or as anticipated from the pharmacological properties of the drug but are not specifically mentioned as occurring with the particular drug under investigation.

9.2 Documenting Adverse Events

All AEs (serious and non-serious) reported by the subject must be recorded on the subject’s study record and entered into the study database no later than 5 days of the site’s first knowledge. The site must report all SAEs to the CRO within 24 hours after first knowledge of the event by the study site. The date of onset, date ended, accurate event term, seriousness, severity, outcome, causality (relationship to study drug), therapy required, and action taken regarding study drug and study participation will be reported for each AE.

Significant LSRs (as judged by the investigator), scarring, and hypertrophic/keloid scars will be captured as adverse events.

9.2.1 Assessment of Severity

The investigator is responsible for evaluating all AEs and determining the severity of the event. Severity will be categorized according to the following definitions:

- Mild: Event may be noticeable to subject; does not influence daily activities; usually does not require intervention
- Moderate: Event may be of sufficient severity to make subject uncomfortable; performance of daily activities may be influenced; intervention may be needed
- Severe: Event may cause severe discomfort; usually interferes with daily activities; subject may not be able to continue in the study; treatment or other intervention usually needed

9.2.2 Assessment of Causality

Several factors should be considered when assessing the relationship (causality) of an event to the study drug or administration of the study drug. The investigator should assess the relatedness to the study drug using a standard of a reasonable possibility of a causal relationship between the study drug and the AE, as per the examples in [Table 8](#):

Table 8 Assessment of Causality

Related Events: Include those assessed as definitely, possibly, or probably related events
	
 • Reasonable temporal sequence to drug administration • Event can be fully attributable to administration of the study drug • Known pharmacological action of the study drug • Specific tests available (positive allergy test, antibodies, metabolites) • As adverse drug reaction in the product information (Investigator’s Brochure) • Reported in the literature as a possible side effect • Dechallenge (event abates on discontinuation of the study drug/without treatment) • Rechallenge positive (event reappears on re-exposure to study drug) • Not explained otherwise by the subject’s clinical state or medical history or by other concomitant agents/therapies, etc.

Unrelated Events: Include those assessed as unlikely or unrelated events
	
 • No reasonable temporal sequence to study drug administration • Event is explained by a number of other factors such as a subject’s clinical state, medical history, or other concomitant agents/therapies • Etiology has been clarified and is in no way related to the study drug • No reason for suspecting a causal relationship to the study drug and • Investigators have established this beyond reasonable doubt

9.2.3 Reporting Serious Adverse Events

Any SAE, whether deemed drug-related or not, must be reported to the CRO as soon as possible after the investigator or coordinator has become aware of its occurrence. The investigator/

coordinator must notify the CRO within 24 hours of notification of the event. When appropriate, Novan will notify the appropriate regulatory body of drug related SAEs.

If a subject experiences an SAE or pregnancy, the investigator must:

1. Report the SAE or pregnancy immediately (within 24 hours) after the investigator becomes aware of the event.
2. Complete an SAE or pregnancy notification form and send the appropriate reporting form to the CRO within 24 hours of knowledge of the event.
3. Obtain and maintain all pertinent medical records, information and medical judgments of medical personnel who assisted in subject's treatment and follow-up and document as appropriate.
4. Provide a more detailed report to both the CRO and the IRB, if applicable, no later than seven days after the investigator discovers the event as further information becomes available, and when necessary update the information with follow-up information including outcomes. This report should include a statement as to whether the event was or was not related to the use of study drug.
5. The investigator will notify the IRB of the SAE or pregnancy according to specific IRB requirements.
6. The investigator will collect information on SAEs until the subject's health has returned to baseline status, until all parameters have returned to normal, or remaining health issues have otherwise been explained.
7. The investigator is responsible for following pregnancies through the end of the pregnancy and for providing the assessment of the healthy live birth or for reporting any abnormal pregnancy outcome such as stillbirth, miscarriage, or deformity to the CRO/sponsor.

For clarity on how to record an adverse event that progresses into a serious adverse event, there should be two events recorded: the first event would be the beginning adverse event, and the second event would be the serious adverse event (i.e. only the time the AE qualified as serious). Resolution of the SAE should be recorded in the same manner, two end dates for SAE and AE, where the SAE and AE may or may not share the same end date.

9.3 Adverse Event Follow-up

AEs that are not resolved at the time of the last scheduled study visit (Week 24/ET2) must be recorded in the study database as ongoing/not recovered/not resolved/resolving. Treatment related adverse events and serious adverse events, including LSRs and scars/keloids, will be followed until resolution or up to 1 year after last treatment, whichever is sooner.

The investigator should follow all SAEs until the events are resolved, or the subject completes study participation at Week 24/ET2. Resolution means the subject has returned to the baseline state of health, or the investigator does not expect any further improvement or worsening of the subject's condition.

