Subjects who discontinue the study prior to the Week 12 visit will be asked to complete the Week 12 visit assessments in the clinic; this will be recorded as an Early Termination (ET1) visit. Subjects who discontinue from the study after Week 12 but prior to Week 24 will be asked to come to the site to complete Week 24 assessments; this visit will be recorded as an ET2 visit.

Safety assessments include BOTE Inflammation Scores, Local Skin Reaction (LSR) scores, adverse event collection, including scarring/keloid and urine pregnancy tests (UPTs). Safety

assessments will be completed at specified visits through Week 12. Adverse events and concomitant medications will be reviewed and updated as needed at each visit through Week 24.

Inflammatory reactions around MC lesions has been associated with imminent resolution of MC (sometimes referred to as “beginning-of-the-end” [“BOTE”] sign). The investigator (or designated evaluator) will assess the presence and overall degree of inflammatory reactions at MC lesions at Baseline (pre-dose) and Weeks 2-12 using the BOTE Inflammation Score (Section 7.1.2.1). BOTE may be associated with itch, but not pain. BOTE is usually asymptomatic, self-limited, localized to individual MC lesions, and does not require discontinuation of study treatment or additional treatment. LSR is generally more diffuse, associated with significant itch or tenderness, may necessitate discontinuation of study treatment, and may need treatment for symptomatic relief (e.g. a topical corticosteroid or topical anesthetic). For very severe LSRs, systemic corticosteroids may be considered (Section 7.2.3 for additional details). Investigators will assess the treatment area at each scheduled visit and use their medical judgement to differentiate between BOTE and LSRs. BOTE Inflammation Score and LSR component scores will be recorded at each visit. When LSRs are clinically significant at the application site, the investigator should report the condition as AE(s).

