Prior to the first application of study drug at Baseline, the investigator will assess the subject’s skin as part of the physical examination, including the presence or absence of individual features of erythema, flaking/scaling, crusting, swelling, vesiculation/pustulation, and erosion/ulceration. At Baseline (30 min. post-dose) and at Week 2 through Week 12 the evaluators will rate LSRs on individual features including erythema, flaking/scaling, crusting, swelling, vesiculation/pustulation, and erosion/ulceration using the LSR Assessment scale (Table 7).

Adverse events will be assessed and collected after the initiation of study drug treatment through the end of the subject’s last visit. Treatment-related adverse events and all serious adverse events will be followed up until resolution or up to one year after last treatment, whichever occurs earlier.

Scar formation (scars/keloids/hypertrophic scars) will be assessed starting at the Week 4 visit through Week 24. The investigator will map locations of the molluscum lesions at Baseline. Additional lesions identified through Week 12 will be added to the map. Using the map as a guidance, the investigator will assess the treated areas for scar/keloid formation. All scars, including keloid/hypertrophic scars, that develop after the Baseline assessment should be captured as AEs and assessed for relatedness to study treatment.

If a subject’s treatment is discontinued by the investigator or the subject because of an AE, that AE should be indicated as the reason for treatment discontinuation. All subjects will be encouraged to remain in the study and to complete all required study visits throughout the 24-week study duration.

A Data Safety Monitoring Board (DSMB) will review all available unblinded safety data (including completed patch testing results). Section 11.2 provides additional details regarding the DSMB.

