6.7.9 Visit 9/Week 24 (Day 169 ± 7 days) (In-clinic Visit)

The following procedures must be performed and recorded at the Week 24 visit.

1. Perform scarring/keloid assessment; if present, document location on lesion map and record as an AE.
2. Complete Investigator Global Severity Assessment and Investigator Global Impression of Change.
3. Complete Subject/Caregiver Global Severity Assessment and Subject Global Impression of Change.
4. Collect and record information for new and ongoing AEs, including subject recurrence of MC.
5. Confirm household MC status (any new cases in household members since last visit visit).
6. Update concomitant medication information.

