6.8 Discontinuation or Withdrawal

6.8.1 Individual Subjects

If at any time during the study the investigator determines that it is not in the best interest of the subject to continue treatment, the subject's treatment will be discontinued. The investigator can discontinue the treatment for a subject at any time if medically necessary. If a subject's treatment is permanently discontinued by the investigator because of an AE, that AE should be indicated as the reason for treatment discontinuation. In this case, the subject is discontinued from the treatment, but still participates in the study and the subject is encouraged to follow the visit schedule and complete all assessments, particularly those at Week 12 and 24.

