7.2.6 Adverse Events

Adverse events will be assessed and collected after the initiation of study drug treatment through the end of the subject's last visit. Treatment-related adverse events and serious adverse events will be followed up until resolution or up to one year after last treatment, whichever occurs earlier.

If a subject's treatment is discontinued by the investigator or the subject because of an AE, that AE should be indicated as the reason for treatment discontinuation. All subjects will be encouraged to remain in the study and to complete all required study visits throughout the 24-week study duration.

If a subject achieves complete clearance at Week 12 or before and experiences new lesions between Week 12 and Week 24, an AE of molluscum contagiosum should be documented to capture this recurrence since there is no lesion count after Week 12.

See [Section 9](#) for additional information regarding adverse events.

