**LSR Score**

Score	Erythema	Flaking/Scaling	Crusting	Swelling	Vesiculation/Pustulation	Erosion/Ulceration
0	Not present	Not present	Not present	Not present	Not present	Not present
1	Slightly pink	Mild, limited	Isolated crusting	Minimal, limited	Fine vesicles	Superficial erosion
2	Pink or light red	Moderate	Crusting < 50%	Mild, palpable	Scant transudate or exudate	Moderate erosion
3	Red, restricted to treatment area	Coarse	Crusting > 50%	Moderate	Moderate transudate or exudate	Marked, extensive
4	Red extending outside treatment area	Scaling extending outside treatment area	Crusting extending outside treatment area	Marked swelling extending outside treatment area	Marked transudate or exudate	Black eschar or ulceration

Adverse events will be assessed and collected after the initiation of study drug treatment through the end of the subject’s last visit. Treatment-related AEs and all serious adverse events will be followed up until resolution or up to one year after last treatment, whichever is sooner.

Scar formation (scars/keloids/hypertrophic scars) will be assessed starting at the Week 4 visit through Week 24. The investigator will map locations of the molluscum lesions at Baseline. Additional lesions identified through Week 12 will be added to the map. Using the map as a guidance, the investigator will assess the treated areas for scar/keloid formation. All scars, including keloid/hypertrophic scars, that develop after the Baseline assessment should be captured as AEs and assessed for relatedness to study treatment.

If a subject's treatment is discontinued by the investigator or the subject because of an AE, that AE should be indicated as the reason for treatment discontinuation. All subjects will be encouraged to remain in the study and to complete all required study visits throughout the 24-week study duration.

When approximately 200 subjects are randomized, a data safety monitoring board (DSMB) will review all available unblinded safety data (including completed patch testing results). The DSMB will provide their recommendation for the study to proceed or not proceed.

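### The protocol gives three different end points for SAE follow-up, and the Week 24/ET2 stop in Section 9.3 is the outlier and the least protective

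*Protocol*

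**What the plan says.** The documents contain three rules for when follow-up of a serious adverse event ends.

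- **Rule A, resolution or one year after last treatment, whichever is sooner.** The first paragraph of Protocol 9.3 says that treatment-related AEs and SAEs "will be followed until resolution or up to 1 year after last treatment, whichever is sooner". Protocol 4.1 says "all serious adverse events will be followed up until resolution or up to one year after last treatment, whichever occurs earlier". Protocol 7.2.6 repeats it: "serious adverse events will be followed up until resolution or up to one year after last treatment". SAP Section 4, below the LSR score table, says "all serious adverse events will be followed up until resolution or up to one year after last treatment, whichever is sooner".
- **Rule B, resolution or Week 24/ET2.** The second paragraph of Protocol 9.3: "The investigator should follow all SAEs until the events are resolved, or the subject completes study participation at Week 24/ET2". The sentence after it counts an event as resolved if the subject is back to baseline health or if the investigator expects no further change.
- **Rule C, no time limit.** The introduction to Protocol Section 9 has SAEs followed to resolution. Protocol 9.2.3, item 6, has the investigator collect SAE information until the subject is back to baseline, values are normal, or what remains is explained.

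The synopsis states the one-year rule for treatment-related AEs only and does not mention SAEs.

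**The concern.** An investigator with an SAE still evolving at the last visit gets three answers: stop now, continue to one year after the last dose, or continue until the event resolves or is explained. The first two come from adjacent paragraphs of one short section. Rule B appears once and nothing else supports it, but it is specific to SAEs and addressed directly to the investigator, so a site could reasonably act on it. Rules A and C also disagree, since one has a cap and the other has none.

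At stake is the outcome of a small number of serious events in a mainly paediatric population, and consistent conduct across about 55 sites. A monitor could not say which conduct is a protocol deviation.

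**Working it through.** The plan gives no figure to reproduce. The check compares the rules and then uses day arithmetic for the distance between Rules A and B.

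**Can the rules be reconciled?**

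1. *Treatment-related* in the first paragraph of 9.3 might qualify both AEs and SAEs, leaving unrelated SAEs to the second paragraph. Protocol 4.1 and SAP Section 4 rule this out, because both apply the one-year rule to all SAEs. Even on that reading the second paragraph covers all SAEs, so a related SAE would still have two end points.
2. Rule B might be meant as a minimum. It does not say that the later of the two events applies; it offers completion at Week 24/ET2 as an alternative end.
3. The definition of resolution takes out stable sequelae. It leaves events that are still changing.
4. Section 9.3 has AEs unresolved at Week 24/ET2 recorded as ongoing. That fixes their status on that date but does not obtain the outcome.

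None of these removes the conflict.

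**Distance between Rule A and Rule B**

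Inputs: Week 12 visit on Day 85 ± 5 (Protocol 6.7.7); Week 24 visit on Day 169 ± 7 (Protocol 6.7.9); one year taken as 365 days; treatment may end early (Protocol 6.8.1: "The investigator can discontinue the treatment for a subject at any time if medically necessary").

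Gap = (day of last dose + 365) − day of last visit.

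| Last dose | Last visit | Gap |
|---|---|---|
| Day 85 | Day 169 | 450 − 169 = 281 days (40.1 weeks) |
| Day 80 | Day 176 | 445 − 176 = 269 days |
| Day 90 | Day 162 | 455 − 162 = 293 days |
| Day 1 | Day 169 | 366 − 169 = 197 days |
| Day 1 | Day 176 | 366 − 176 = 190 days |

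The planned schedule gives 281 days. The visit windows give 269 to 293 for a last dose at Week 12, and the lower end falls to 190 if treatment stops on Day 1. Each figure is the most follow-up that could be lost; an SAE that resolves sooner loses less.

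**How many subjects**

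Protocol Table 2 (Section 2.1.4.2) gives serious TEAEs through Week 24 in the two earlier phase 3 trials: (0 + 0 + 1 + 1) / (116 + 235 + 117 + 237) = 2/705 = 0.28%, exact (Clopper-Pearson) 95% CI 0.03% to 1.02%. Assuming that rate carries over, 850 × 2/705 = 2.4 subjects (0.3 to 8.7). This counts any serious TEAE. Only SAEs unresolved at Week 24/ET2 matter here, and the documents give no figure for that subset.

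**The case against.** The strongest reply is that a site reading the whole protocol would not stop at Week 24. Rule B says the investigator *should* follow SAEs, while 9.2.3 introduces its list with *must* and the other statements use *will*. One softer sentence stands against several firmer ones, and stopping early would breach 9.2.3, item 6. This lowers the practical exposure, but it does not settle the matter: the protocol has no precedence clause, and Rule B is the SAE-specific instruction in the section on follow-up.

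A second reply is that nothing in the analysis depends on it. That stands. Under SAP Section 6 the database is locked once all subjects have completed Week 24/ET2, so later follow-up would not enter the planned tables under any rule.

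A reader might infer three stronger things that the documents do not support.

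- *That 281 days of follow-up would routinely be lost.* The figure applies only to an SAE that stays unresolved for the full year, in a subject whose site relies on Rule B.
- *That the loss is larger still for early leavers.* Protocol 4.1 provides for an earlier last visit: "Subjects who discontinue from the study after Week 12 but prior to Week 24 will be asked to come to the site". But such a subject has left the study, and the listed reasons in Protocol 6.8.3 include withdrawn consent and loss to follow-up. Further follow-up may then be limited by the departure itself.
- *That a known drug risk would go unobserved.* Protocol 2.1.4.2 reports no treatment-related SAE in the earlier phase 3 trials, and 2.1.5 reports none for berdazimer sodium. A related SAE also falls under the one-year rule for treatment-related AEs, so the exposure is mainly to unrelated SAEs.

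**Conclusion.** The inconsistency is real and minor. Rule B is the outlier, since nothing else in either document ends SAE follow-up at Week 24/ET2. It is not the whole problem, though: removing it would still leave a one-year cap in 4.1, 7.2.6 and 9.3 against no cap in Section 9 and 9.2.3. The one-year rule also has no defined end for a subject who was never treated, and Section 9 collects SAEs from consent onwards.

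The gap of about 281 days assumes a last dose on Day 85, a last visit on Day 169 and an SAE that stays unresolved. The small number of subjects assumes that the earlier trials' rate of serious TEAEs is a fair guide. Efficacy results, adverse event tables, power and alpha are unaffected.

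**What to change.** In the second paragraph of Protocol 9.3, delete the alternative that ends follow-up when participation ends at Week 24/ET2. Keep the definition of resolution, and keep the instruction to record events unresolved at the last visit as ongoing.

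Then state one SAE rule in Protocol 4.1, 7.2.6, 9, 9.2.3 (item 6) and 9.3. Either of these would do:

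- follow every SAE until it resolves or is explained, with no cap; or
- follow every SAE until resolution or one year after last treatment, whichever is sooner, and until a stated end point such as resolution in subjects who were never treated.

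The synopsis sentence could name SAEs as well. If the uncapped rule is chosen, the descriptive sentence in SAP Section 4 should be changed to match; no analysis in the SAP is affected.

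The cost is a few sentences of wording, submitted to the IRB as an amendment under Protocol 12.1.3. Scheduled visits and sample size do not change.
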